1.3 Schedule of Activities (SoA)

Study Period	Screening	Intervention Period 21-Day Cycles						EOT	Post Intervention Visits			Notes
		Cycle 1		Cycle 2		Cycle 3 Onward			Safety FU ^a	Efficacy FU	Survival FU	
		1	8	15	1	15	1					
Scheduling Window (Days)		-28 to -1	±3	±3	±3	±3	±3		At DC	30 Days After Last Dose (± 7 d)	q9w ^b (± 7 d)	q12w (± 7 d)
Administrative and General Procedures												
Informed Consent	X											Consent form can be documented at any time before any protocol-specific screening procedures are performed. If the investigator plans to treat beyond disease progression, additional consent is required.
Inclusion/Exclusion Criteria	X											
Participant Identification Card	X											
Demographics	X											
Staging	X											At initial diagnosis and at study entry
Medical/Surgical History	X											

Study Period	Screening	Intervention Period 21-Day Cycles						EOT	Post Intervention Visits			Notes
		Cycle 1		Cycle 2		Cycle 3 Onward			Safety FU ^a	Efficacy FU	Survival FU	
Cycle Number/Day		1	8	15	1	15	1		30 Days After Last Dose (+ 7 d)	q9w ^b (± 7 d)	q12w (± 7 d)	
Scheduling Window (Days)	-28 to -1	±3	±3	±3	±3	±3	±3	At DC				
Prior/Concomitant Medication Review	X	X	X	X	X	X	X	X	X	X		Concomitant medications received within 30 days before the first dose of study intervention through 30 days after the last dose (or 90 days if used to treat an SAE) will be recorded.
Subsequent antineoplastic treatment									X	X	X	All anticancer therapy will be recorded until time of death or termination of survival follow-up. If a clinical visit is not feasible, follow-up information may be obtained via telephone or email.
Allocation/randomization via IRT		X										Participants will be allocated/randomized on C1D1 (-3d) after confirmation of eligibility. All procedures and assessments on C1D1 should be performed after allocation/randomization.

Study Period	Screening	Intervention Period 21-Day Cycles						EOT	Post Intervention Visits			Notes
		Cycle 1			Cycle 2		Cycle 3 Onward		Safety FU ^a	Efficacy FU	Survival FU	
		1	8	15	1	15	1		30 Days After Last Dose (+ 7 d)	q9w ^b (± 7 d)	q12w (± 7 d)	
Scheduling Window (Days)	-28 to -1	±3	±3	±3	±3	±3	At DC					

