
 • EORTC QLQ-C30 • EORTC QLQ-disease-specific: 
 • Breast (QLQ-BR23) • Ovarian (QLQ-OV28) • Gastric (QLQ-STO22) • Colorectal (QLQ-CR29) • GBM (QLQ-BN20) • Biliary (QLQ-BIL21) • Pancreatic (QLQ-PAN26) • EuroQol (EQ)-5D-5L 		X		X		X	X	X				
PRO assessments will be collected at baseline, every cycle through Cycle 13, Cycle 17, Cycle 21, EOT, and at the 30-day Safety FU visit.
 
ePROs will also be obtained at the treatment discontinuation visit and the 30-day Safety Follow-up Visit.
 
If the treatment discontinuation visit occurs 30 days from the last dose of study treatment, at the time of the mandatory Safety Follow-up Visit, ePROs do not need to be repeated.
 
See additional details in Section 8.2.2.
	

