6.3 Measures to Minimize Bias: Randomization and Blinding

6.3.1 Intervention Assignment

Intervention allocation/randomization will occur centrally using an IRT system. There are 2 study intervention arms. Participants in Cohorts A through G will be allocated to receive pembrolizumab + lenvatinib (Arm 1), with the following exception. The last approximately 60 participants in Cohort D will be assigned randomly in a 1:1 ratio to pembrolizumab + lenvatinib (Arm 1) or lenvatinib monotherapy (Arm 2).

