6.3.3 Blinding

This is an open-label study; therefore, the Sponsor, MSD, investigator and participant will know the treatment administered.

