8.2.2 Patient-reported Outcomes

Health-related QoL will be assessed at Cycle 1 Day 1 (before the first dose of study intervention), every cycle through Cycle 13, Cycle 17, Cycle 21, at the time of discontinuation (EOT Visit), and the 30-day Safety Follow-up Visit (See SoA in Section 1.3 for electronic patient-reported outcomes [ePRO] administration schedule). If the EOT Visit occurs 30 days from the last dose of study treatment, a Safety Follow-up Visit is not required, ePROs do not need to be repeated.

HRQoL questionnaires will be administered by trained site personnel and completed electronically by participants in the following order: EORTC QLQ-C30 first, then the cohort-specific ePROs listed below, and EuroQoL EQ-5D last:

- Breast (QLQ-BR23)
- Ovarian (QLQ-OV28)
- Gastric (QLQ-STO22)
- Colorectal (QLQ-CR29)
- GBM (QLQ-BN20)
- Biliary (QLQ-BIL21)
- Pancreatic (QLQ-PAN26)

It is best practice and strongly recommended that electronic patient-reported outcomes (ePROs) are administered to allocated participants prior to drug administration, AE

evaluation, and disease status notification. If the participant does not complete the ePROs at a scheduled time point, the MISS_MODE form must be completed to capture the reason the assessment was not performed.

If at the time of enrollment of a participant, the translated version of any PRO measure is not available for that language/country, and therefore cannot be completed by the participant at Cycle 1 Day 1, then the PRO measure will not be required for this participant at any point during the study. The other study PRO measures must be completed as scheduled.

NOTE: For some sites, the translated PRO measure might become available after study startup and should be administered to participants at their time of enrollment; for some sites, the PRO measure translation might not be available for the entire duration of the study.

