9.2 Responsibility for Analyses/In-house Blinding

The statistical analysis of the data obtained from this study will be the responsibility of the Clinical Biostatistics department of the Sponsor.

This study is being conducted as an open-label study, ie, participants, investigators, and Sponsor personnel will be aware of participant treatment assignments after each participant is enrolled and treatment is assigned. Although the study is open label, analyses or summaries generated by randomized intervention assignment, or actual intervention received will be limited and documented. Independent radiologist(s) will perform the central imaging review without knowledge of participant-level treatment status.

For Cohort D (CRC), the last 60 participants will be randomized in a 1:1 ratio between Arm 1 and Arm 2. The Sponsor will generate the randomized allocation schedule(s) for study intervention assignment for this protocol, and the randomization will be implemented in IRT.

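### The only baseline quality-of-life assessment is scheduled after open-label randomisation, so in the randomised part of Cohort D it can be coloured by knowledge of the arm

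*Combined protocol and SAP*

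**What the plan says.** Section 1.3, in the row for allocation via IRT, fixes the timing: "Participants will be allocated/randomized on C1D1 (-3d) after confirmation of eligibility". The same note continues: "All procedures and assessments on C1D1 should be performed after allocation/randomization".

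The PRO row of that table gives the schedule: "PRO assessments will be collected at baseline, every cycle through Cycle 13, Cycle 17, Cycle 21, EOT, and at the 30-day Safety FU visit". Section 8.2.2 places the baseline: "Health-related QoL will be assessed at Cycle 1 Day 1 (before the first dose of study intervention". No screening PRO is described in either place. Section 8.2.2 also recommends that the ePROs "are administered to allocated participants prior to drug administration", and before AE evaluation and news of disease status. It says nothing about completing them before the arm is known.

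On blinding, Section 6.3.3 states that "the Sponsor, MSD, investigator and participant will know the treatment administered", and Section 9.2 that "participants, investigators, and Sponsor personnel will be aware of participant treatment assignments after each participant is enrolled and treatment is assigned".

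Only one group has an arm to learn. Section 6.3.1 says: "The last approximately 60 participants in Cohort D will be assigned randomly in a 1:1 ratio", to the combination (Arm 1) or lenvatinib alone (Arm 2).

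**The concern.** A baseline should precede the event whose consequences it is used to measure. Here the questionnaire follows assignment, and in an open-label comparison assignment is itself news. A participant told that pembrolizumab is or is not included may answer emotional, role or global health items differently that day, and the direction may depend on the arm.

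Section 3 uses the baseline for change scores and plans time to deterioration in the QLQ-C30 subscales. Section 9.5.3 admits to the PRO population only participants with a baseline score. A baseline that differs between arms because of assignment would feed into these summaries in the randomised part of Cohort D.

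Section 8.2.2 already accepts the principle: it tries to keep drug administration, AE discussion and disease news from colouring the answers. Knowledge of the arm is the same kind of influence and is not covered.

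**Working it through.** The plan states no figure on this point, so there is none to reproduce. The check is of the order of events, then of who is affected, then of what an arm-specific reaction would do.

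**Order of events.**
- Allocation or randomisation: C1D1, or up to 3 days before (Section 1.3). Section 8.1.9 likewise has treatment start within 3 days of it.
- Participant aware of the arm: once it is assigned (Section 9.2). No text holds the result back.
- Baseline PRO: C1D1, before the first dose (Section 8.2.2), and after allocation under the Section 1.3 note.

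I found no text that exempts the ePRO or requires it before disclosure. Section 8.1.8 describes all participants as allocated without randomisation. That conflicts with Sections 4.1.1, 6.3.1 and 9.2 on Cohort D and needs reconciling; I have followed the latter three.

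**Who is affected.** From Section 9.1, Cohort D is 30 + 40 + 60 = 130. The first 70 all receive Arm 1. The randomised share is 60/130 = 46%, or about 30 per arm. In the other cohorts and the first 70 of Cohort D there is one regimen, so allocation tells the participant nothing new.

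**Effect on change scores.** Let r0 and rt be the between-arm differences in mean reaction to assignment at baseline and at visit t. The between-arm difference in change from baseline is then in error by

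rt − r0.

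- Reaction gone by visit t (rt = 0): error −r0, the full baseline shift.
- Reaction half gone (rt = r0/2): error −r0/2.
- Reaction unchanged (rt = r0): error 0.

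With adjustment for baseline and a within-arm slope β (equal to the correlation if the two visits have equal SDs), the error is rt − β·r0. For illustration, assume r0 of 0.1 to 0.3 SD and β of 0.3 to 0.7. In the faded case the size falls from 0.1–0.3 SD to between 0.3 × 0.1 = 0.03 SD and 0.7 × 0.3 = 0.21 SD. Adjustment shrinks the error there but does not remove it. If the reaction persists, adjustment leaves (1 − β)·r0.

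The same algebra applies within an arm. Arm 2's own change from baseline would carry its own reaction. Arm 1 of Cohort D would mix about 70 participants for whom the regimen was no news with about 30 for whom it was. Time to deterioration is affected in the same way if deterioration is defined as a worsening from baseline; the definition is left to the sSAP.

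**Scale against precision.** With 30 per arm, the 95% half-width for a between-arm difference in means is 1.96 × √(2/30) = 0.51 SD. If the SD were 20 to 25 points on a 0–100 scale (assumed), that is about 10 to 13 points. The assumed reaction of 0.1 to 0.3 SD lies inside it.

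**The case against.** The strongest reply is that little depends on this. PROs are exploratory and analysed per tumour cohort (Section 3). The objective comparing the combination with monotherapy lists ORR, DCR, DOR, PFS and OS, not PROs. Section 9.5.1 describes the randomised-subcohort comparison for efficacy only, and Section 9.8 rules out hypothesis testing. Section 9.4.3 says PRO scales will be summarised, with details in the sSAP, and part of Section 9.6 is redacted. A by-arm PRO contrast can be neither confirmed nor excluded. All of this stands, and it limits the weight of the point.

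It is also fair to say that an earlier baseline does not cure open-label reporting. With r0 = 0 the change contrast carries rt in full, so a lasting reaction still enters later scores. What the earlier baseline removes is contamination of the reference value.

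A reader might infer something stronger: that every randomised participant is obliged to answer after learning the arm, that the whole shift biases every visit, and that no adjustment helps. The documents do not support that.
- The note says *should*, and the moment at which the site tells the participant is not fixed. Knowledge before the questionnaire is likely, not certain in each case.
- The full shift is carried only where the reaction has faded.
- Baseline adjustment reduces the error in that case.
- Not every PRO summary is anchored on baseline: Section 3 also lists the global score and EQ-5D-5L utilities.
- Any shift in points, such as 2 to 5, is an assumption; the visible text gives no PRO SD or effect.

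**Conclusion.** The ordering is documented and nothing visible overrides it. About 60 randomised Cohort D participants can, and probably will, give their only baseline PRO after learning their arm. A reaction that differs by arm would contaminate that baseline and bias exploratory change-from-baseline and time-to-deterioration summaries there by the later reaction minus the baseline reaction.

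The size cannot be determined from the documents. Under the assumptions above it is at most 0.1 to 0.3 SD unadjusted where the reaction fades, against a half-width of 0.51 SD. This is a minor point: the primary ORR, the sample size and the single-regimen groups are unaffected. It is worth acting on because the remedy costs almost nothing.

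**What to change.** Amend the Section 1.3 note so that every C1D1 procedure *except the baseline ePRO set* follows allocation. Add one line to Section 8.2.2: at least for the randomised part of Cohort D, and most simply for everyone, the baseline ePRO is completed at C1D1 or up to 3 days earlier, before the IRT assignment is made or disclosed.

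For participants already randomised, use the sSAP to report the timing of the baseline ePRO relative to the IRT assignment, and caveat any by-arm PRO summary in Cohort D. An analysis excluding baselines taken after disclosure should not be relied on: if sites followed the current note, it may leave few or no participants.

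The cost is two sentences of text, ePRO access before allocation, and a few questionnaires from people who are then not allocated. No visit, questionnaire or participant is added.

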Hematology and chemistry laboratory assessment	X			X	X		X	X	X		Performed locally within 7 days before start of treatment. Every effort should be made to collect samples at the same time of day. LDH is only required at screening.	
Urine dipstick testing	X			X	X	X	X	X	X		Performed locally within 7 days before the start of treatment. Urinalysis may be used if the use of urine dipsticks is not feasible. Participants with >1+ (30 mg/dL) proteinuria on urine dipstick during screening will undergo 24-hour urine collection for quantitative assessment of proteinuria. Participants with urine protein ≥1 g/24-hour will not be eligible. See Section 6.6.2.2 for management of proteinuria.	

Study Period	Screening	Intervention Period 21-Day Cycles						EOT	Post Intervention Visits			Notes
		Cycle 1			Cycle 2		Cycle 3 Onward		Safety FU ^a	Efficacy FU	Survival FU	
Scheduling Window (Days)		1	8	15	1	15	1		30 Days After Last Dose (+ 7 d)	q9w ^b (± 7 d)	q12w (± 7 d)	
PT or INR, aPTT and Fibrinogen	X							At DC				Screening samples collected within 7 days of treatment initiation. Additional testing to be conducted as clinically indicated for participants taking anticoagulant therapy.
T3, FT4, TSH	X			X				X	X			At Screening, C2D1, then every 2 cycles thereafter. Screening samples to be collected within 7 days of treatment initiation. Free T3 is acceptable where T3 cannot be determined.
Pregnancy test (WOCBP only)	X			X		X	X	X	X			WOCBP require a negative test before randomization and within 24 hours before to the first dose of study intervention. If less than 24 hours have elapsed between the randomization test and the first dose of study intervention, another pregnancy test is not required.

Study Period	Screening	Intervention Period 21-Day Cycles						EOT	Post Intervention Visits			Notes
		Cycle 1		Cycle 2		Cycle 3 Onward			Safety FU ^a	Efficacy FU	Survival FU	
Cycle Number/Day		1	8	15	1	15	1		30 Days After Last Dose (+ 7 d)	q9w ^b (± 7 d)	q12w (± 7 d)	
Scheduling Window (Days)	-28 to -1	±3	±3	±3	±3	±3	±3	At DC				
HIV, HBsAg, HCV	X											Testing is not required unless mandated by local health authority.
Pharmacokinetics/Biomarkers												
Pembrolizumab PK		X			X		X*					*Predose C1D1, C2D1, and C8D1 only; Cohorts A-F only.
Pembrolizumab antidrug antibodies		X			X		X*					*Predose C1D1, C2D1, and C8D1 only; Cohort A-F only.

Study Period	Screening	Intervention Period 21-Day Cycles						EOT	Post Intervention Visits			Notes

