6.6.2 Lenvatinib

Lenvatinib dose reduction and interruption for participants who experience lenvatinib- or lenvatinib-pembrolizumab combination therapy-related toxicity will be in accordance with the dose modification guidelines described in [Table 5](#). An interruption of study treatment for more than 28 days will require Sponsor approval before treatment can be resumed.

The starting dose of lenvatinib is 20 mg/day for participants enrolled in the combination therapy arm (Arm 1). Lenvatinib dose reductions for Arm 1 occur in succession based on the previous dose level (14, 10, and 8 mg/day). Any dose reduction below 8 mg/day must be discussed with the Sponsor.

The starting dose of lenvatinib is 24 mg/day for participants enrolled in the monotherapy arm (Arm 2). Lenvatinib dose reductions for Arm 2 will take place in succession based on the previous dose level (20, 14, and 10 mg/day). Any dose reduction below 10 mg/day must be discussed with the Sponsor.

For both Arm 1 and Arm 2, once the lenvatinib dose has been reduced, it may not be increased at a later date, unless the dose has been mistakenly decreased; in this situation, the Sponsor's approval is required to increase the dose.

Refer to the subsections below for management of hypertension (Section 6.6.2.1), proteinuria (Section 6.6.2.2), diarrhea (Section 6.6.2.3), hepatotoxicity (Section 6.6.2.4), thromboembolic events (Section 6.6.2.5), posterior reversible encephalopathy syndrome/reversible posterior leukoencephalopathy syndrome (PRES/RPLS; Section 6.6.2.6), hypocalcemia (Section 6.6.2.7), hemorrhage (Section 6.6.2.8), gastrointestinal perforation or fistula formation (Section 6.6.2.9), QT prolongation (Section 6.6.2.10), and osteonecrosis of the jaw (Section 6.6.2.11) as appropriate, before consulting the dose modification table ([Table 5](#)). For overlapping toxicities of pembrolizumab and lenvatinib, please refer to Section 6.6.3.

See Section 10.7 (Appendix 7) for country-specific requirements.

Table 5 Dose Modification Guidelines for Lenvatinib-Related Adverse Events

Treatment-Related Toxicity ^{a,b}	Management	Dose Adjustment
Grade 1 or Tolerable Grade 2		
	Continue treatment	No change
Intolerable Grade 2^{c,d} or Grade 3^{e,f}		
First occurrence	Interrupt lenvatinib until resolved to Grade 0-1, or tolerable Grade 2	Arm 1: Reduce lenvatinib dose from 20 mg QD to 14 mg QD (1-level reduction) Arm 2: Reduce lenvatinib dose from 24 mg QD to 20 mg QD (1-level reduction)

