6.6.3 Dose Modifications for Overlapping Toxicities

Based on the known toxicity profiles of pembrolizumab and lenvatinib, certain treatment-related AEs are uniquely associated with one drug versus the other. For example, hypertension, arterial thrombotic events, proteinuria, and hemorrhagic events are known risks for lenvatinib treatment, while immune-related AEs are risks for pembrolizumab treatment. However, certain AEs, such as such as diarrhea, hypothyroidism, and liver enzyme elevation, may be initially considered attributable to either study drug. Therefore, evaluation of attribution is important for determining the study drug most likely related to the AE, or an alternative etiology, and subsequently proper clinical management. The following aspects should be considered:

1. Timing of AE onset

Since lenvatinib is dosed daily and continuously due to a relatively short half-life (28 hours), and pembrolizumab is dosed Q3W due to a long half-life, lenvatinib can be interrupted to assess whether an AE improves/resolves with dechallenge (ie, interruption of treatment) based on the following 2 scenarios:

- If an AE is identified during a treatment cycle (ie, between 2 pembrolizumab doses), only lenvatinib dose interruption is needed.
- If an AE is identified at the beginning of a treatment cycle, lenvatinib can be interrupted and dosing of pembrolizumab should be held.

If the participant recovers from an AE in response to lenvatinib interruption (ie, positive dechallenge), the event is more likely to be related to lenvatinib. Otherwise, after excluding other alternative explanations, an immune-related AE should be considered.

2. Severity of AE

If an AE is suspected to be treatment-related and is severe/life-threatening at the time of onset or is rapidly worsened, action including interrupting both drugs and initiating treatment with a corticosteroid (with exception of hypothyroidism, T1DM) and other supportive care should be taken promptly.

3. Participants receiving the combination therapy (pembrolizumab + lenvatinib) must discontinue study therapy if any of the following occur:

- ALT or AST >5 X ULN for more than 2 weeks.

Pembrolizumab will have already been permanently discontinued per [Table 3](#), but lenvatinib may be administered at a reduced dose by the time this criterion is met and must be permanently discontinued immediately.

- ALT or AST $>3 \times$ ULN and (TBL $>2 \times$ ULN or INR >1.5)

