Although [Table 3](#) advises pembrolizumab to be withheld (interrupted), and [Table 5](#) advises lenvatinib to have no dose modification or a reduction, if this criterion is met, both drugs must be permanently discontinued immediately.

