- Any progression or recurrence of any malignancy, or occurrence of another malignancy that requires active treatment. Exceptions to secondary malignancy include basal cell carcinoma of the skin, squamous cell carcinoma of the skin, new nonulcerated primary melanoma <1 mm in depth with no nodal involvement, or carcinoma in situ (eg, breast carcinoma, cervical cancer in situ) that have undergone potentially curative therapy. Exceptions should be discussed with the Sponsor before continuing therapy or remaining in follow-up.
- Confirmed radiographic disease progression outlined in Section 8.2.1.5 or Section 8.2.1.6.

Note: Participants will be permitted to continue treatment beyond iRECIST- or RANO-defined progression (Arm 1 only) after confirming informed consent addendum has been documented and after Sponsor consultation.

- Unacceptable AE(s).

A participant may be discontinued from study intervention but continue to be monitored in the study for the following reason:

- PD as determined by the investigator.

Note: Participants will be permitted to continue treatment beyond RECIST 1.1- or RANO-defined progression (Arm 1 only) as long as investigator-assessed clinical stability is observed, the participant is tolerating study intervention (Section 8.2.1.5 or Section 8.2.1.6) and after obtaining documented informed consent addendum. Treatment beyond confirmed PD per iRECIST or RANO may be permitted on Sponsor consultation.

Participants receiving the combination therapy (pembrolizumab + lenvatinib) must discontinue study therapy if any of the following occur:

ALT or AST elevation meeting the following criteria:

- ALT or AST $>5 \times$ ULN for more than 2 weeks

Pembrolizumab will have already been permanently discontinued per [Table 3](#) but lenvatinib may be administered at a reduced dose by the time this criterion is met and must be permanently discontinued immediately.

- ALT or AST $>3 \times$ ULN and (TBL $>2 \times$ ULN or INR >1.5)

Although [Table 3](#) advises pembrolizumab to be withheld (interrupted), and [Table 5](#) advises lenvatinib to have no dose modification or a reduction, if this criterion is met, both interventions must be permanently discontinued immediately.

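### Arm 1's mandatory stop at ALT/AST >3 x ULN with INR >1.5 has no required on-treatment INR; in a narrow group off anticoagulants, detection rests on general clinical discretion

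*Combined protocol and SAP*

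**What the plan says.** Section 6.6.3 (item 3) lists two liver criteria on which participants receiving the combination must stop study therapy. The second is ALT or AST above 3 x ULN together with TBL above 2 x "ULN or INR >1.5". INR is a separate limb, so it triggers the stop even when bilirubin is normal. The section adds that, although Table 3 only withholds pembrolizumab at this level and Table 5 "advises lenvatinib to have no dose modification or a reduction, if this criterion is met, both drugs must be permanently discontinued immediately". Section 7.1 repeats the rule: "if this criterion is met, both interventions must be permanently discontinued immediately".

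The SoA (Section 1.3) schedules PT or INR once, at screening within 7 days of starting treatment. Its note for later visits reads: "Additional testing to be conducted as clinically indicated for participants taking anticoagulant therapy". Appendix 2, Table 15, footnote i has the same restriction. ALT, AST and bilirubin belong to the chemistry panel, which the SoA repeats throughout treatment.

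**The concern.** A mandatory stop works only if the values that define it are measured. The bilirubin limb and the >5 x ULN rule use scheduled tests. The INR limb does not, and the only INR-specific instruction after screening concerns participants on anticoagulants. A site that follows the SoA and Table 5 exactly could therefore keep giving lenvatinib to someone who meets a permanent-stop criterion, while a site that orders an INR would stop both drugs. What is at stake is participant safety and uniform use of a stop rule.

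**Working it through.** No sample size or error rate is involved. The check sets the stop rule against every place where an INR could be scheduled or triggered.

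**1. Where on-treatment testing is ordered**

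| Place | What it orders | Names INR? |
|---|---|---|
| SoA, PT/INR row | Screening; later as indicated, on anticoagulants | Yes, but PT alone satisfies it |
| Appendix 2, Table 15, footnote i | Same as the SoA | Same |
| SoA, chemistry row | ALT, AST, bilirubin at C1D15, C2D1 and Day 1 of each cycle from Cycle 3 | No |
| Section 6.6.1.1 text | Adequate evaluation of suspected irAEs | No |
| Table 3, AST/ALT row | Liver function tests, weekly or more often to be considered | No |
| Section 6.6.2.4 | Liver tests, listed as ALT, AST and bilirubin; close monitoring | No |
| Section 8.4.7, hepatic event of clinical interest | Triggered only if TBL is at least 2 x ULN | No |
| Section 8 and Appendix 2 general text | Extra tests may be done if judged necessary | No |
| Section 10.3.5 | Obliges medically indicated supplemental work-up | No |

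The extracted PT/INR row also shows an end-of-treatment label. It appears to be a displaced column header. Even a real draw there would come after the decision to stop.

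**2. The band in which the gap can occur**

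- Above 5 x ULN for more than 2 weeks, Section 6.6.3 says: "Pembrolizumab will have already been permanently discontinued per" Table 3. Table 3 takes that action for Grade 3 or 4.
- At the criterion in question, Section 6.6.3 says that Table 3 withholds pembrolizumab, which is its Grade 2 action.
- The uncovered band is therefore >3 to 5 x ULN. The protocol does not print this grade boundary; it is inferred from these two statements.
- In Table 5, "Grade 1 or Tolerable Grade 2" means that lenvatinib continues unchanged. Intolerable Grade 2 or Grade 3 interrupts it.

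**3. Counts that can be made**

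- On-treatment draws through Cycle 35 that carry ALT, AST and bilirubin: 1 (C1D15) + 1 (C2D1) + 33 (C3D1 to C35D1) = 35.
- Required on-treatment INR draws: 0.
- Planned participants to whom the rule applies: A 30 + B 30 + C 100 + D (70 + 30) + E 100 + F 100 + G 100 = 560. Adding the 30 in Arm 2 gives the stated 590.

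**4. Overlap with eligibility**

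Table 1 admits ALT/AST up to 5 x ULN in participants with liver metastases or biliary tract cancer, so the transaminase half of the rule can be met at entry. Table 1 limits INR to 1.5 x ULN, while the stop rule uses an absolute 1.5. The two differ wherever the laboratory ULN for INR exceeds 1.0. The documents give no ULN. If it is assumed to be 1.1 to 1.2, the entry ceiling off anticoagulants is 1.5 x 1.1 = 1.65 to 1.5 x 1.2 = 1.80, above the stop threshold.

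**The case against.** The strongest reply is that the protocol does supply the means. Section 10.3.5 obliges the investigator to arrange medically indicated work-up; it does not merely allow it. Section 6.6.3 itself names INR as deciding once ALT/AST exceeds 3 x ULN, so the investigator is told which test matters. This largely stands. What is missing is an explicit trigger. But the duty turns on a judgement of medical indication, and the only INR-specific schedule points to a different group, so practice may vary between sites.

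The second reply is that little is left uncovered. Pembrolizumab is withheld at Grade 2. Item 1 of Section 6.6.3 says "lenvatinib can be interrupted to assess whether an AE improves/resolves with dechallenge". For severe or rapidly worsening events, item 2 calls for "action including interrupting both drugs and initiating treatment with a corticosteroid". The bilirubin limb and the >5 x ULN rule remain. This stands as a limit on size, but the dechallenge is optional and item 2 does not reach a tolerable Grade 2 event.

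Third, the laboratory manual, the Investigator Study File Binder and the product labels to which France and Canada refer are not among the documents and could contain INR guidance. That caveat stands. Nothing in the protocol text shows that they do.

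A reader might go further and infer that no INR is ever required, or that the INR limb cannot be operated. The documents do not support either. A PT or INR is required of everyone at screening, and general clauses permit, and where indicated oblige, further testing.

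**Conclusion.** The point holds in a limited form: in Arm 1 the INR limb has no required on-treatment INR. The gap concerns a participant off anticoagulants with ALT/AST >3 to 5 x ULN, TBL no higher than 2 x ULN, lenvatinib continuing as tolerable Grade 2, and no INR ordered at the investigator's initiative. The conclusion assumes that the unseen manuals add no INR trigger and that the grade boundary is as inferred from Section 6.6.3.

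The number affected cannot be derived. A reader might take 560 or 35 as its size, but 560 is the reach of the rule and 35 counts chemistry draws; neither measures the exposed group. A reader might also infer bias in response or safety endpoints. The documents give no basis for that, and none is claimed. The weight lies between a minor wording point and a recommended change. It is worth making mainly because it is cheap.

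**What to change.** Add one sentence to the SoA PT/INR row and the same sentence to Appendix 2 footnote i, which would otherwise still restrict later testing to anticoagulated participants:

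> In Arm 1 participants not taking an anticoagulant that raises INR, obtain a local INR (not PT alone) when on-treatment ALT or AST exceeds 3 x ULN and TBL is <=2 x ULN.

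The form follows reflex tests already in the protocol: a 24-hour urine collection when UPCR is at least 2.4 (Section 6.6.2.2), and direct bilirubin when total bilirubin is above ULN (Table 15). The bilirubin condition avoids testing when the stop is already triggered. Limiting the test to participants off such anticoagulants means that the stop rule itself need not change. Exempting anticoagulated participants from the INR threshold would be a separate, debatable relaxation and is not needed here.

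The cost is one local coagulation tube at a liver-test draw. In a participant with liver metastases or biliary tract cancer who stays above 3 x ULN it could recur, at up to 35 scheduled draws through Cycle 35, plus any unscheduled ones. Because of the eligibility overlap shown above, the test may also reveal a few participants who met the stop criterion at baseline and would have to stop with no change since entry. The sponsor should note this when adding the test.
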